iChoose+. *iChoose+* is conceptualized to more accurately reflect the contact frequency and program duration of *Bright Bodies* which included weekly nutrition (parent/child together), behavioral (parent/child independently), and exercise (2/week; child only) session for 24 weeks. For an additional 24 weeks all *Bright Bodies* sessions continued to be delivered, but on a bi-weekly schedule. *iChoose+* will contain the following components: (1) Clear communication *iChoose* workbooks for parents and children that provide the basis for all *iChoose* activities to assist families in changing physical activity, eating behaviors, and child weight status; (2) 12 family classes that reduce reading demands and incorporate numerous non-print education strategies, hands-on demonstrations, and pictorial instructions (each 2-hour class will be split evenly

IRB-HSR # 19748: A randomized-controlled trial to compare the reach, effectiveness and maintenance of two family-based childhood obesity treatment programs in a medically underserved region

between nutrition, exercise, and behavior change topics); (3) 12 IVR calls that provide reinforcement of class objectives, personalization of goals, and apply teach-back and teach-to-goal methods (two versions of each call will be used—one call for families that attended the class and one for those that did not); (4) 48 family exercise sessions to promote practice and mastery and encourage social support (six PA sessions are integrated within the family class for a total of 2 sessions/week); and (5) bi-weekly child newsletters to reinforce class messages and provide fun family activities. To increase the duration and contact after the initial 24 weeks, we will continue with a 6-month maintenance program, including bi-weekly IVR calls to parents and newsletters to children. The IVR structure will focus on relapse prevention through the reinforcement of program content and skill building opportunities while also allowing for goal setting and feedback relative to nutrition and physical activity outcomes.

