Community Advisory Board members were identified and named when the PCORI application was submitted:

- Representatives from organizations in the Dan River Region who have a child-focused organizational mission, invited as a stakeholder
- ≥18 years of age
- Willing and able to provide informed consent

Parent Advisory Team members:

- Parent who previously participated in a childhood obesity program and/or are the parent of a child ages 5-12 years of age
- ≥18 years of age
- live in the Dan River Region

2. List the criteria for exclusion

Parent/child dyads:

- children with a major cognitive impairment based on medical record review or contraindications for physical activity
- families that are already participating in a childhood obesity treatment program

Community Advisory Board: none

Parent Advisory Team:

- Cannot simultaneously be enrolled in the comparative effectiveness trial and serve on the Parent Advisory Team

3. List any restrictions on use of other drugs or treatments.

Parent/child dyads

- families that are already participating in a childhood obesity treatment program will be excluded

Community Advisory Board and Parent Advisory Team: NA

Statistical Considerations

1. Is stratification/randomization involved?

Yes

► IF YES, describe the stratification/ randomization scheme.

We will use simple randomization, at the parent-child dyad level. Randomization is not blinded. The researchers will have access to the randomization scheme.

► IF YES, who will generate the randomization scheme?

Sponsor
 UVa Statistician. Answer/Response:

UVa Investigational Drug Service (IDS)
 X Other: [name], statistician from Virginia Tech

2. What are the statistical considerations for the protocol?

- The primary end-point is 6-month reduction in BMI z-score.
- We calculated a standardized effect size relative to the differences in BMI z-scores and standard deviations *related to 6-month BMI z-score reduction* for *Family Connections* (0.07) and *Bright Bodies* as a target for the *iChoose+* condition (BMI z-score reduction = 0.16).

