A letter of support is provided from SOVAH Pediatrics and PATHS.

Biomedical Research

1. What will be done in this protocol?

Parent/Child Dyads.

Families have an equal chance of being randomly assigned to any one of the two programs. They cannot choose to which program they are assigned.

GROUP 1: iChoose

The iChoose program will last for 12 months. During the first six months families will be asked to:

- Attend 12 small group education sessions every other week. The health classes are for both the parent and child and will include information on nutrition and exercise.
- Attend one hour family exercise sessions two times a week (total of 48 sessions, 12 of which are part of the small group education sessions)
- Complete 12 automated telephone calls to provide support to help families reach your eating and physical activity goals.
- The child will also get 12 mailed newsletters to help them meet their program goals.

During the last six months of the program parents will continue to get support calls every other week (a total of 12 more calls) and your child will get 12 more newsletters.

See additional study procedures listed in #2 below.

GROUP 2: Family Connections

The Family Connections program will last for 6 months. During this time parents will be asked to:

- Attend 2 education sessions that are one week apart. The health classes are for parents/guardians only and will include information on parental role modeling regarding healthy nutrition and exercise behaviors.
- Complete 10 automated telephone calls to provide support families reach your eating and physical activity goals. There will be 2-3 calls per month during months 1-3 and then 1 call per month during months 4-6.

Community Advisory Board and Parent Advisory Team. Meeting procedures provided above in the study design section. (NOTE: the meetings are not part of the research procedures, only the mixed-methods evaluation, as described below. The participation in meetings is a contractual arrangement for advisory board members).

2. List the procedures, in bullet form, that will be done for RESEARCH PURPOSES as stipulated in this protocol.

IRB-HSR # 19748: A randomized-controlled trial to compare the reach, effectiveness and maintenance of two family-based childhood obesity treatment programs in a medically underserved region

Interventions: The iChoose and Family Connections interventions are described above and in the study design section.

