If a subject withdraws they will not participate in any additional qualitative interviews involved with the Community Advisory Board and Parent Advisory Team capacity evaluation. Their previous recorded information, prior to when they withdraw, will still be used. If a participant withdraws who previously had a photo release form, we will not use their photographs for any additional promotional purposes effective the date of study withdrawal.

Data and Safety Monitoring Plan

Adverse events will only be collected or recorded if a causal relationship to the study intervention is suspected. If any adverse event is considered serious and unexpected, the event must be reported to the IRB-HSR within 7 days from the time the study team receives knowledge of the event.

1. Definitions

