1.1 How will you define adverse events (AE)?

An adverse event will be considered any undesirable sign, symptom or medical condition considered **related to the intervention**. Medical condition/diseases present before starting the intervention will be considered adverse events only if they worsen after starting the study and that worsening is considered to be related to the study intervention. An adverse event is also any undesirable and unintended effect of research occurring in human subjects as a result of the collection of identifiable private information under the research.

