1.4 What is the definition of a data breach?

A data breach is defined in the HITECH Act (43 USC 17932) as an unauthorized acquisition, access, or use of protected health information (PHI) that compromises the security or privacy of such information.

2. What risks are expected due to the intervention in this protocol?

Expected Risks related to study participation	Pick One
There is a small risk that breaches of privacy and/or confidentiality might occur. The risk of violation of subject privacy and confidentiality is minimal due to the requirements of the privacy plan in this protocol.	Occurs rarely
Serious side effects from being involved in an exercise program if participants have not been physically active are rare, but should be considered. 
• Cardiovascular events (e.g., heart attack)• Respiratory issues (e.g., asthma, shortness of breath)• Muscle and/or bone injuries	Occurs rarely
Stress or anxiety in completing questionnaires	Occurs rarely

3. When will recording and reporting of unanticipated problems/adverse events begin?

After subject begins study intervention

4. When will the recording/reporting of unanticipated problems/adverse events end?

Subject completes participation in the protocol

5. Data and Safety Oversight Responsibility

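### Recorded adverse events cannot be fairly compared between arms: recording depends on suspected relatedness, programme contact with the child is very unequal, and no common adverse event question is listed

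*Combined protocol and SAP*

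**What the plan says.** The Data and Safety Monitoring Plan opens with the recording rule: "Adverse events will only be collected or recorded if a causal relationship to the study intervention is suspected". Item 1.1 builds the same condition into the definition: "An adverse event will be considered any undesirable sign, symptom or medical condition considered" related to the intervention. A pre-existing condition counts only if it worsens and the worsening is judged related. Events that are serious and unexpected go to the IRB within 7 days. Recording runs from the start of the intervention to the end of participation, with no distinction between arms.

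On masking, Statistical Considerations, item 1, says: "Randomization is not blinded. The researchers will have access to the randomization scheme".

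On contact with the child, Biomedical Research, item 1, asks iChoose+ families to "Attend 12 small group education sessions every other week", parent and child together, and to come to exercise sessions twice a week ("total of 48 sessions, 12 of which are part of the small group education sessions"). Study Design: Biomedical, item 1, describes the overlap differently: "six PA sessions are integrated within the family class for a total of 2 sessions/week". In Family Connections there are 2 sessions, and "The health classes are for parents/guardians only"; the rest is 10 automated calls.

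On expected harms, the risk table in the Data and Safety Monitoring Plan, item 2, says: "Serious side effects from being involved in an exercise program if participants have not been physically active are rare, but should be considered". It lists cardiovascular, respiratory, and muscle or bone events. The Risk/Benefit Analysis ties the main risk to iChoose+ by name.

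Biomedical Research, item 2, lists what is collected at 3, 6 and 12 months in both arms. No adverse event question appears there, nor among the stated topics of the 3-month parent interview.

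**The concern.** Two filters act before an event reaches the data set. Someone must learn of it, and someone must suspect that the programme caused it. Both can differ by arm. Staff see iChoose+ children at many sessions, some of them exercise, where an injury would be witnessed or mentioned. The documented physical risks are exercise risks linked to that arm, so the same injury may be attributed more readily there. An event judged unrelated is by definition not an adverse event, so no record is left for anyone to reconsider.

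The results are meant to help local partners decide which programme to continue, and readers tend to take any table of adverse events as comparative. A higher count in iChoose+ could reflect closer observation. A low count in either arm could reflect events dismissed one at a time. Statistical Considerations, item 2, also sets early stopping aside on the ground that no clear negative consequences are expected. Counts collected under this rule are a weak test of that expectation.

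**Working it through.** **Inputs from the documents**
- iChoose+ classes attended by the child: 12.
- iChoose+ exercise sessions: 2 per week over the first 24 weeks.
- Exercise sessions held inside classes: 12 (Biomedical Research, item 1) or 6 (Study Design: Biomedical, item 1). These two statements conflict and must be reconciled; both are carried through.
- Family Connections sessions attended by the child: 0.
- Post-baseline assessments common to both arms: 3 (at 3, 6 and 12 months).
- Planned size: about 87 dyads per arm.

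**1. The plan's own figure.** 2 × 24 = 48 exercise sessions, as stated.

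**2. Distinct programme occasions with the child** = classes + exercise sessions − sessions held inside classes.
- iChoose+, 12 inside classes: 12 + 48 − 12 = 48.
- iChoose+, 6 inside classes: 12 + 48 − 6 = 54.
- Family Connections: 0.

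**3. Adding the common assessments.**
- iChoose+: 48 + 3 = 51, or 54 + 3 = 57.
- Family Connections: 0 + 3 = 3.
- Ratio: 51/3 = 17, or 57/3 = 19.

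These are scheduled contacts, not attendance.

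**4. What unequal recording could do (illustration only).** The event and recording rates below are assumptions; the documents give none and rate these risks as rare. Expected recorded count = 87 × true rate × proportion recorded, with the same true rate in both arms.

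| True rate | Recorded, iChoose+ / Family Connections | Expected counts | Ratio |
|---|---|---|---|
| 10% | 90% / 90% | 7.8 / 7.8 | 1.0 |
| 10% | 60% / 30% | 5.2 / 2.6 | 2.0 |
| 10% | 90% / 30% | 7.8 / 2.6 | 3.0 |
| 10% | 90% / 10% | 7.8 / 0.9 | 9.0 |
| 5% | 90% / 30% | 3.9 / 1.3 | 3.0 |
| 20% | 90% / 30% | 15.7 / 5.2 | 3.0 |

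For example, 87 × 0.10 × 0.90 = 7.8 and 87 × 0.10 × 0.30 = 2.6. The true rate cancels from the ratio, which is simply the ratio of recording proportions. The table shows how a spurious difference would arise, not how large it is in this trial.

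**The case against.** The case for the plan is a serious one. This is a minimal-risk behavioural trial, and the exercise is described as no harder than everyday recreation. Limiting collection to suspected-related events is a recognisable, proportionate choice. No aim, hypothesis or analysis compares harms. The Risk/Benefit Analysis says local decisions will draw on adherence, effectiveness, maintenance and sustainability. Unanticipated problems have their own reporting route, and an external member has a role in monitoring adverse events.

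Much of this stands, and it rules out several stronger readings that a reader might infer:

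- *Family Connections children are not observed.* They attend no programme sessions, but research staff assess children in both arms at 3, 6 and 12 months, and both arms have evaluation interviews at 6 and 12 months. Parent health advisors are also planned across both conditions. The evaluation instruments are attachments not reproduced in the document, so whether they elicit problems is unknown.
- *Harms cannot be compared at all.* Weight is measured on one schedule in both arms, as are blood pressure, waist and quality of life at baseline, 6 and 12 months. These do not capture the injuries and acute events in the risk table, so the limitation concerns recorded adverse events.
- *An injury in Family Connections would never be recorded.* That arm also promotes physical activity, and the threshold is only suspicion, so such an event could be recorded.
- *Unmasked staff judge causality.* This is likely in an open trial with no masked assessor described, but the documents do not name the assessor.

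The oversight argument does not remove the point. On adverse events, the external member and the at-least-annual review can consider only what passed the recording rule.

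**Conclusion.** The point holds as a limitation of the safety plan. Recorded adverse event counts will not support a fair comparison between arms, because recording is conditional on suspected relatedness in an open trial, scheduled contact with the child is 51 to 57 occasions against 3 (48 to 54 against 0 for programme sessions alone), and no uniform question is listed at the common assessments. The contact counts come directly from the documents and hold under either statement of how many exercise sessions fall inside the classes.

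The size of any resulting bias is unknown. The 2- to 9-fold ratios in the illustration rest wholly on assumed recording proportions. It would be wrong to read this as an internal contradiction or as a failure to deliver a promised analysis, since no comparison of harms is promised. It does not touch the primary BMI z-score analysis. It is worth acting on because the remedy is cheap.

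**What to change.** At the 3-, 6- and 12-month assessments in both arms, ask every parent the same short question about injuries and medically attended events since the last assessment. For Cohort 3 at 12 months, put it on the mailed form, because questionnaires moved to paper for that time point. Record all answers regardless of suspected cause, code relatedness in a separate field, and tabulate by arm. Leave IRB reporting unchanged.

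For assessments already past, state the limitation and make no between-arm claim from recorded adverse events. This may cover most of the trial: the version in hand is dated 22 April 2020, and the planned timeline has Cohorts 1 and 2 finished by March 2019 and Cohort 3 starting in February 2019.

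The cost is one item on existing contacts and some coding, with no extra visits. The remedy is not complete. It relies on recall over up to six months by parents who know their programme, so some reporting difference between arms could remain.

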1.1 How will you define adverse events (AE)?

An adverse event will be considered any undesirable sign, symptom or medical condition considered **related to the intervention**. Medical condition/diseases present before starting the intervention will be considered adverse events only if they worsen after starting the study and that worsening is considered to be related to the study intervention. An adverse event is also any undesirable and unintended effect of research occurring in human subjects as a result of the collection of identifiable private information under the research.

1.2 How will you define an unanticipated problem?

An unanticipated problem is any issue that involves increased risk(s) to participants or others. This means issues or problems that cause the subject or others to be placed at greater risk than previously identified, even if the subject or others do not incur actual harm. For example if a subject's confidentiality is compromised resulting in serious negative social, legal or economic ramifications, an unanticipated problem would need to be reported. (e.g., serious loss of social status, loss of job, interpersonal conflict.)

1.3 What are the definitions of a protocol violation and/or noncompliance?

A protocol violation is defined as any change, deviation, or departure from the study design or procedures of research project that is NOT approved by the IRB-HSR prior to its initiation or implementation. Protocol violations may be major or minor violations.

IRB-HSR # 19748: A randomized-controlled trial to compare the reach, effectiveness and maintenance of two family-based childhood obesity treatment programs in a medically underserved region

Noncompliance can be a protocol violation OR deviation from standard operating procedures, Good Clinical Practices (GCPs), federal, state or local regulations. Noncompliance may be serious or continuing

Additional Information: see the IRB-HSR website at

http://www.virginia.edu/vpr/irb/HSR_docs/Forms/Protocol_Violations_%20Enrollment_Exceptions_Instructions.doc

1.4 What is the definition of a data breach?

A data breach is defined in the HITECH Act (43 USC 17932) as an unauthorized acquisition, access, or use of protected health information (PHI) that compromises the security or privacy of such information.

2. What risks are expected due to the intervention in this protocol?

Expected Risks related to study participation	Pick One
There is a small risk that breaches of privacy and/or confidentiality might occur. The risk of violation of subject privacy and confidentiality is minimal due to the requirements of the privacy plan in this protocol.	Occurs rarely
Serious side effects from being involved in an exercise program if participants have not been physically active are rare, but should be considered. 
• Cardiovascular events (e.g., heart attack)• Respiratory issues (e.g., asthma, shortness of breath)• Muscle and/or bone injuries	Occurs rarely
Stress or anxiety in completing questionnaires	Occurs rarely

3. When will recording and reporting of unanticipated problems/adverse events begin?

After subject begins study intervention

4. When will the recording/reporting of unanticipated problems/adverse events end?

Subject completes participation in the protocol

5. Data and Safety Oversight Responsibility

5.1. Who is responsible for overseeing safety data for this study?

No additional oversight body other than PI at UVa

All site PI's (*for protocols in which there is no common protocol but data from multiple sites will be combined for analysis: Collaborative Site Analysis Studies*)

The UVa Cancer Center Data and Safety Monitoring Committee

Medical Monitor

DSMB/ DSMC

Research Monitor:

Other: Per our funded protocol: Study oversight will be provided by the MPI's ([name] and [name]), Co-I's and Project Director and two qualified external (not on the study team or CAB and will likely be the same two SOVAH Pediatrics and Parks & Rec external members outlined above) members: 1) one with the role of evaluating the progress of the study, monitor adherence to research protocols in recruitment and intervention phases, and monitoring adverse events and, 2) an analyst who will monitor the integrity of analytic work.

5.2. What is the composition of the reviewing body and how is it affiliated with the sponsor?

Members of the study team may NOT also be members of the DMSB.

Information may be found in the UVa Cancer Center Institutional DSMP

Collaborative Site Analysis Study- see CSAS section of this DSMP

Other- See Above. There is no affiliation with the PCORI sponsor.

5.3. What items will be included in the aggregate review conducted by the PI?

NA- PI is not the overall person overseeing the safety data for this study.

All adverse events

Unanticipated Problems

Protocol violations/Issues of noncompliance

IRB-HSR # 19748: A randomized-controlled trial to compare the reach, effectiveness and maintenance of two family-based childhood obesity treatment programs in a medically underserved region

Audit results

Application of dose finding escalation/de-escalation rules
These should be outlined under 2.4.

Application of study designed stopping/decision rules

Early withdrawals

Whether the study accrual pattern warrants continuation/action

Endpoint data

Other: Specify Answer/Response:

5.4 How often will aggregate review occur?

For additional information on aggregate review see:
www.virginia.edu/vpr/irb/hsr/continuations.html#aggreview

NA- PI is not the overall person overseeing the safety data for this study.

Per Enrollment/Events

Annually

Semi-Annually

Quarterly

Monthly

Other: Specify Answer/Response:

5.5. How often will a report, regarding the outcome of the review by the DSMB/DSMC, be sent to the UVa PI?

A copy of these reports must be sent to the IRB if applicable as soon as they are received by the PI. Do not wait until the next continuation to submit them to the IRB.

NA- PI is not the overall person overseeing the safety data for this study.

Per Enrollment/Events

Annually

Semi-Annually

Quarterly

Monthly

Other: Specify Answer/Response:

IRB-HSR # 19748: A randomized-controlled trial to compare the reach, effectiveness and maintenance of two family-based childhood obesity treatment programs in a medically underserved region

5.6. How will a report of the information discussed in question 5.4 OR 5.5 be submitted to the IRB?

Part of IRB-HSR continuation status form
 Separate report from DSMB/DSMC or UVa PI
 Other: **Specify** **Answer/Response:**

5. What is your plan for safety monitoring?

Safety monitoring and aggregate review of adverse events, unanticipated problems, protocol violations and any data breach will be performed by the PI and IRB-HSR through continuation review at least annually.

6. What is your plan for reporting a Unanticipated Problem, Protocol Violation or Data Breach?

Type of Event	To whom will it be reported:	Time Frame for Reporting	How reported?
Unanticipated Problems that are not adverse events or protocol violations This would include a Data Breach.	IRB-HSR	Within 7 calendar days from the time the study team received knowledge of the event.	Unanticipated Problem report form. http://www.virginia.edu/vprgs/irb/HSR_docs/Forms/Reporting_Requirements-Unanticipated_Problems.doc
Protocol Violations/Noncompliance (The IRB-HSR only requires that MAJOR violation be reported, unless otherwise required by your sponsor, if applicable.) OR Enrollment Exceptions	IRB-HSR	Within 7 calendar days from the time the study team received knowledge of the event.	Protocol Violation, Noncompliance and Enrollment Exception Reporting Form http://www.virginia.edu/vprgs/irb/hsr_forms.html Go to 3rd bullet from the bottom.
Data Breach of Protected Health Information	The UVa Corporate Compliance and Privacy Office ITC: if breach involves electronic data	As soon as possible and no later than 24 hours from the time the incident is identified. As soon as possible and no later than 24 hours from the time the incident is identified.	UVa Corporate Compliance and Privacy Office- [contact] ITC: Information Security Incident Reporting procedure,

	Police if breach includes items that are stolen: Stolen on UVA Grounds OR Stolen off UVA Grounds- contact police department of jurisdiction of last known location of PHI	IMMEDIATELY.	http://www.itc.virginia.edu/security/reporting.html Police: phone- [contact]
--	--	--------------	--

Payment

1. Are subjects being reimbursed for travel expenses?

No

2. Are subjects compensated for being in this study?

Yes

Parent and child dyad:

Both the parent and the child will each receive a gift card for their time involved in each of the health screenings, including:

- beginning of the program (baseline): \$25 gift card
- 3 month follow-up: \$25 gift card
- 6 month follow-up: \$50 gift card
- 12 month follow up: \$50 gift card

Community Advisory Board and Parent Advisory Team: are not compensated completing the mixed-methods evaluations. Some are paid members of the study team, but additional individual payment is not provided for completion of the mixed-methods evaluation.

2a. What is the maximum TOTAL compensation to be given over the duration of the protocol?

Child \$150; Parent \$150

2b. Explain compensation to be given.

Children and parent will receive a Wal-Mart gift card. We have worked in this region for 7 years and this is always the most favorable form of compensation. There is immense value in having immediate compensation for their time involved in the health screenings. Also, this study populations are transient and are relatively difficult to track. Mailing, tracking and troubleshooting mailed payments will cause added burden to the research staff.

2c. Is payment pro-rated?

Yes. Parents and children can attend any of the health screenings/date collection and receive the compensation. They do not have to participate in any the program or in all of the health screening to qualify for compensation when they do attend the health screenings.

2d. Is money paid from UVa or State funds (including grant funds) or will items such as gift cards be distributed through UVa?

Yes, PCORI sends money to OSP and contracts to cover the cost of compensation to be given to subjects.

2d(i). How will the researcher compensate the subjects?

X Gift card/Debit Card

2d(ii). Which category/ categories best describes the process of compensation?

X Compensation will include an alternative method (petty cash, gift card, other) and tax information will be collected, securely stored, and submitted electronically to Procurement Services as required.

► If this box is checked and an alternate method will be used, justify why you are unable to issue checks through the UVa Oracle or state system.

We have worked in this region for 7 years and Wal-Mart gift cards are always the most favorable form of compensation. There is immense value in having immediate compensation for their time involved in the health screenings. Also, these study populations are transient and are relatively difficult to track. Mailing, tracking and troubleshooting mailed

payments will cause added burden to the research staff.

IMPORTANT: If you check this box you will be required to submit the subjects' name, Social Security number, full address and amount of payment to Procurement at the end of each calendar year. The Office of the VP for Research will send you instructions on this procedure at a later date.

Risk/ Benefit Analysis

1. What are the potential benefits for the participant as well as benefits which may accrue to society in general, as a result of this study?

Parent/child dyads:

Participants will gain information about improving health behaviors and weight through the education sessions, physical activity sessions, telephone calls, and newsletters. The primary benefit participants may experience is education and personalized goal setting and monitoring that may result in improvements in diet and increase in physical activity. This information might lead to lifestyle changes which could result in decreased weight status and improved health status. At each of the health screenings, participants will receive a handout that explains the results of their Body Mass Index (BMI) results. During the group education sessions participants will receive a personal action plan, workbooks, educational handouts, and other small incentives such as water bottles and measuring cups. Below is an example list of incentives and price for each items:

- Water Bottles \$1.50
- T-Shirts \$2.00
- MyPlates \$5.00
- Draw-String Bags \$1.70
- UNO cards \$4.00
- Jump Ropes \$2.00
- Stress balls \$2.00

Community Advisory Board and Parent Advisory Team:

For members of the Community Advisory Board and Parent Advisory Team, there is no guarantee of benefits for participating in this study. However, understanding perceptions of capacity will help promote equity among all members. In turn, this will improve the likelihood of developing a collaborative team, and one that can successfully implement and sustain a childhood obesity reduction initiative in the Dan River Region. The potential direct benefit of Phase 1 is the development of two childhood obesity

IRB-HSR # 19748: A randomized-controlled trial to compare the reach, effectiveness and maintenance of two family-based childhood obesity treatment programs in a medically underserved region

treatment programs that could be sustained in the region and fill a current gap in healthcare.

When local evidence is available to stakeholder and parents regarding differences in adherence, effectiveness, and maintenance of the two programs (*iChoose+* vs Family Connections), along with data regarding the potential for system sustainability, informed decisions can be made to help reduce childhood obesity disparities in the medically underserved DRR. It is hoped that the information gained from this study may be helpful for the future treatment of childhood obesity and sustainability of evidence-based programs in the Dan River Region.

2. Do the anticipated benefits justify asking subjects to undertake the risks?

Yes, the anticipated benefits justify the risks.

Parent/child dyads:

There are minimal risks for participants involved in this study. The main risk of taking part in this program is a small risk associated with starting a physical activity program with *iChoose+* if participants have not been physically active.

The other risks are the inconvenience of time and potential discomfort of participating in the health screening. It is possible that completing the assessments could cause stress or anxiety; however, the questionnaires contain minimally sensitive questions. Nonetheless, all community based project staff and university research assistants will be trained to deal with this anticipated anxiety and each individual will always have the right to refuse to participate or to answer any questions on the survey.

Community Advisory Board and Parent Advisory Team:

